7.4.7 Echocardiograms (Part B Only)

Summary statistics (n, mean, median, SD, minimum, maximum) will be presented for the baseline measurement of Left Ventricular Ejection Fraction.

The number of patients with clinically significant changes in systolic function will be tabulated for each on-study assessment separately by ascending ALN-GO1 dose level and regimen and placebo for the single-blind dosing period.

All ECHO assessments will be listed by subject in the order of ascending ALN-GO1 dose and placebo.

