4.5. Blinding

This is a single-blind, placebo-controlled study; therefore, only the study subjects/patients will be blinded to treatment assignment. Patients in Part B dosed monthly will be unblinded on or after Day 78 in order for patients and their families to be better prepared for the transition to receive ALN-GO1 if initially randomized to placebo. Patients dosed quarterly will be unblinded to initial treatment assignment following completion of the postdose follow-up period. The Investigators, Medical Monitors at the Sponsor and CRO, clinical study center personnel, pharmacokineticist, and members of the SRC will have knowledge of the treatment assignment. The clinical study center pharmacy staff will maintain the single-blind according to clinical study center-specific procedures and the Pharmacy Manual. Syringes containing dispensed study drug will be masked in the pharmacy before transfer to the clinic.

During the blinded period, if the subject/patient becomes seriously ill during the study, and the treating physician determines that the clinical management of the subject requires that the subject know the study drug assignment, the Investigator may break the blind, as necessary. If time permits, clinical study center personnel should contact the Medical Monitor before unblinding to discuss the need to unblind the subject/patient. A record of when the blind was broken, who broke the blind, and why it was broken, will be maintained in the Trial Master File.

See the Pharmacy Manual for additional details.

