5.2.2. Additional Exclusion Criteria for Part B

20. Clinical evidence of systemic oxalosis, including but not limited to, myocardial dysfunction, bone marrow, bone, or eye infiltration with oxalate as determined by the Investigator
21. For patients <18 years old, diastolic and/or systolic blood pressure equal to or greater than the 95th percentile for age, gender, and height (see Appendix 11.4 Table 14 and Table 15) after 10 minutes of rest at screening.
22. Echocardiography (Echo) assessment of abnormal left ventricular systolic function, defined as left ventricular ejection fraction <55% at screening
23. Troponin I greater than the upper limit of normal (ULN) at screening (abnormal results should be repeated)

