8.2.7. Safety Analyses

The primary safety parameter is the incidence of AEs. Safety will also be evaluated through vital signs, ECGs, clinical laboratory assessments, and physical examinations; Echo assessments will be evaluated in Part B only. ADAs will also be analyzed.

AEs will be summarized by the MedDRA System Organ Class and Preferred Term (Version 16, or higher). Prior and concomitant medications will be classified according to the World Health Organization (WHO) drug dictionary.

Separate tabulations of the incidence of treatment emergent adverse events (TEAEs), TEAEs by maximum severity, treatment-related AEs, SAEs, and discontinuation due to AEs will be provided. By-subject listings will also be provided for any deaths, SAEs and AEs leading to discontinuation.

Descriptive statistics will be provided for clinical laboratory data and vital signs data, presented as both actual values and changes from baseline over time. Clinical laboratory assessment shift tables from baseline to worst post-values will be presented. Abnormal physical examination findings, ECG, and Echo (Part B only) data will be presented in a by-patient data listing.

Descriptive statistics will be provided for ECG interval data and presented as both actual values and changes from baseline relative to each on-study evaluation and to the last evaluation on study. Details of any abnormalities will be included in patient listings.

ADA results will be provided in a by-patient data listing.

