6.1.6 Echocardiograms (Part B Only)

ECHO assessments will be performed according to instructions provided in a study manual at select time points outlined in the Schedule of Assessments. The Investigator or designee is responsible for reviewing the ECHOs to assess whether the results have changed since the Screening/Baseline visit and to determine the clinical significance of the results.

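### On-study LVEF is listed but not summarised, and the only on-study echo table is an unblinded clinical-significance count confined to the single-blind period

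*SAP*

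**What the plan says.** SAP 7.4.7 plans three echo outputs for Part B:

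- LVEF summary statistics (n, mean, median, SD, minimum, maximum), which "will be presented for the baseline measurement of Left Ventricular Ejection Fraction".
- A count: "The number of patients with clinically significant changes in systolic function will be tabulated for each on-study assessment separately". The sentence goes on to give the breakdown and the period of this table: "by ascending ALN-GO1 dose level and regimen and placebo for the single-blind dosing period".
- A listing: "All ECHO assessments will be listed by subject in the order of ascending ALN-GO1 dose and placebo".

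On who makes the judgement, SAP 6.1.6 states: "The Investigator or designee is responsible for reviewing the ECHOs to assess whether the results have changed since the Screening/Baseline visit". The same person decides clinical significance. Protocol 4.5 names the investigators in the same list in which "members of the SRC will have knowledge of the treatment assignment", and Protocol 4.1 also describes them as unblinded. Neither document gives a numerical definition of a clinically significant on-study change.

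LVEF is nevertheless treated as a number at entry: exclusion criterion 22 in Protocol 5.2.2 rules out abnormal systolic function, "defined as left ventricular ejection fraction <55% at screening".

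For echo output the protocol asks for less than the SAP does. Section 8.2.7 states: "Abnormal physical examination findings, ECG, and Echo (Part B only) data will be presented in a by-patient data listing".

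**The concern.** Safety is the primary objective. The rationale for Protocol Amendment 3 says that echo and troponin I were added to Part B on the Safety Review Committee's recommendation, after a Phase 3 study of another of the sponsor's RNAi products was stopped for a mortality imbalance that was mainly cardiac. The measure brought in for that reason gets less on-study summary than its neighbours. The SAP gives actual values and changes from baseline for ECG intervals (7.4.6), laboratory tests including troponin I (7.4.3 with 6.1.7) and vital signs (7.4.4).

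A count of clinically significant changes is a coarse measure. It discards the size and direction of every change below the assessor's own bar, and here the assessor knows the treatment. A consistent modest fall across patients could leave the table showing zeros. The restriction to the single-blind period adds a second gap, because most scheduled on-study echoes fall outside it.

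**Working it through.** The plan states no figure for this point, so there is nothing to reproduce. The check has three steps.

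**1. Which echoes can enter the count.** SAP 7.2.1 ends the single-blind period at Study Day 85 for patients randomised to ALN-GO1, and before the first ALN-GO1 dose for placebo patients. The echo rows were read by counting columns and checked against the troponin I rows and footnotes.

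| Schedule | On-study echoes | Inside the single-blind period |
|---|---|---|
| Table 2, monthly | Day 85; Day 169, then about every 168 days | Day 85 only |
| Table 3, monthly, placebo to open label | Day 85 (predose), Day 169, Day 253, then about every 168 days | Day 85, as the placebo value |
| Table 4, quarterly | Day 113; Day 197, then about every 168 days | none |

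The Day 113 placement in Table 4 rests on alignment. It is supported by the troponin footnote, which names Days -1, 85, 113 and 197; the echo mark shares the Day 113 column.

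**2. How many patients that is.** In the SAP 7.2.3 layout, each of two monthly dose levels has 3 single-blind active patients, so the count has 2 × 3 = 6 active patients. Each monthly cohort of 4 (3:1) has one placebo patient, so 2 placebo patients contribute. The combined monthly total reaches 16 if both cohorts are expanded: 6 single-blind + 2 crossing over from placebo + 2 × 4 expansion patients on open-label drug. The last two groups have no on-drug echo in the count.

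**3. What a count can miss, and what a mean can show.** Both parts use assumed values that are not in the documents: an SD of LVEF change of 4 to 6 points, normal changes, and, for the count, a patient flagged at a fall of at least 10 points.

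With mean fall μ and SD σ, the chance that a patient is flagged is p = 1 − Φ((10 − μ)/σ), and the chance that none of 6 is flagged is (1 − p)^6.

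| Mean fall (points) | p, SD 4 to 6 | Chance of zero flagged among 6 |
|---|---|---|
| 3 | 0.040 to 0.122 | 0.78 to 0.46 |
| 5 | 0.106 to 0.202 | 0.51 to 0.26 |
| 7 | 0.227 to 0.309 | 0.21 to 0.11 |

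The 95% half-width of a mean change is t(0.975, n − 1) × SD/√n.

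| n | Where it arises in SAP 7.2.3 | Half-width, SD 4 to 6 |
|---|---|---|
| 3 | one monthly dose, single-blind | 9.9 to 14.9 |
| 4 | one dose, combined, not expanded | 6.4 to 9.5 |
| 6 | monthly single-blind total | 4.2 to 6.3 |
| 16 | monthly combined total, both cohorts expanded | 2.1 to 3.2 |

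A mean fall of 4 to 5 points is therefore within noise at a single dose level, borderline at best in the single-blind total, and distinguishable only in the fully expanded combined total.

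**The case against.** The strongest reply is that nothing is lost and nothing promised is missing. Most of its parts stand.

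- A reader might infer that on-study cardiac function is reported only as a yes/no judgement. It is not: every echo is listed by subject, Part B has at most 24 patients, and ECG intervals and troponin I are summarised over time.
- A reader might infer that a fall in LVEF could reach no table. A fall judged clinically significant in the single-blind period is counted. Under Protocol 7.5.7.2, a finding relevant to patient safety is recorded as an adverse event, and so reaches the adverse event tables.
- A reader might infer a departure from the protocol. Protocol 8.2.7 promises only a listing for echo, so the SAP already goes further.
- A reader might infer that a change table would settle the matter. Step 3 shows that it would not at dose level.
- A reader might infer that LVEF is free of the assessment bias. Echoes follow a study manual that is not among the documents. Who reads LVEF, and whether blinded, is not stated. A number still keeps the size and direction of change, which the count discards.
- The count sentence could be read so that the single-blind limit applies to placebo alone. That would close the period gap, but LVEF would still not be summarised after baseline.

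The argument from listings does not dispose of the point. Laboratory, vital-sign and ECG data are also listed in the same small sample, and the SAP summarises them as well.

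**Conclusion.** The point holds as a gap in summary presentation. On-study LVEF has no planned summary, and the one on-study echo table is a judgement by unblinded investigators, without a stated threshold, that reaches about 6 active and 2 placebo patients at one visit. A fall not called clinically significant, or occurring after Day 85, would be visible only in listings unless recorded as an adverse event. It is worth correcting because echo was added for cardiac safety in a trial whose primary objective is safety.

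The conclusion rests on three assumptions: that the Table 4 echo mark belongs to Day 113; that the single-blind limit applies to the whole count table; and that numeric LVEF is recorded at each on-study echo, which is plausible but not stated. The probabilities and half-widths are illustrations on an assumed SD and flagging rule. The documents do not support reading this as lost data or as a failure of cardiac monitoring.

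**What to change.** Add to SAP 7.4.7:

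*LVEF actual value and change from baseline will be summarised at each scheduled on-study echo by regimen and ALN-GO1 dose level, with a combined ALN-GO1 total and pooled placebo where available, across the ALN-GO1 dosing and follow-up periods. Baseline is that for the treatment being received (Section 4.3.1).*

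Keep the investigator-judged count and state plainly which periods it covers.

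The pieces are already in place. Under SAP 4.3.1, monthly placebo patients would use the predose Day 85 echo as their ALN-GO1 baseline. Their later echoes then line up with those of patients randomised to active: 169 − 85 + 1 = Day 85 and 253 − 85 + 1 = Day 169. Quarterly placebo patients have no scheduled echo between screening and their Day 85 dose, so the screening value serves. Their Day 113 echo is 113 − 85 + 1 = Day 29 on drug, so the separate one-dose and two-dose quarterly columns of SAP 7.2.3 should be kept.

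The cost is one descriptive table, with no new procedure and no test, if numeric LVEF is already captured. Check this first against the echo manual and case report form. An on-study count below 55% is optional: criterion 22 uses that value for eligibility only.

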 - f. Vital signs (blood pressure, pulse rate, body temperature, and respiration rate) will be measured in the supine position after the patient has rested comfortably for 10 minutes. On Day 85 only, vital signs will be measured within 2 hours predose; and 30 (±5 minutes) and 4 hours (±15 minutes) postdose.

- g. All 12-lead ECGs are triplicate, using centralized equipment. ECGs will be measured approximately 5 minutes apart. Recordings will be obtained after the patient has rested comfortably in the supine position for approximately 10 minutes. Patients should remain supine between ECGs. On dosing days, ECGs will be measured within 2 hours predose; and at 1 hour (± 20 minutes), 2 hours (± 20 minutes), and 4 hours (± 20 minutes) postdose. On all other days, ECGs should be collected at approximately the same time of day corresponding to the predose collection (± 1 hour).
- h. Echo will be performed during the first visit of the Safety and PD Follow-up Period (Day 253), and thereafter, approximately every 168 days corresponding with visits to the clinical study center for the duration of the study.
- i. Pregnancy tests will be performed for women of childbearing potential only. A serum pregnancy test will be performed after the onset of menarche if the patient was not of childbearing potential at screening, and a serum or urine pregnancy test will be performed per the Schedule of Assessments and any time pregnancy is suspected. The results of the pregnancy test must be known before ALN-GO1 administration.
- j. Biochemistry, hematology, coagulation, LFTs, and urinalysis parameters are described in Section 7.5.6. Clinical laboratory tests will be analyzed by a central laboratory. Within 4 days prior to dosing, LFT measurements will be analyzed by a local laboratory and confirmed by a central laboratory. Local clinical laboratory results for LFT measurements must be available and reviewed by the Investigator before study drug administration.

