 - e. During screening and at EOT, height will be measured for all patients; thereafter, height will only be measured for patients <18 years of age. Additionally, for patients <18 years of age, at each time point, height will be measured in centimeters, and in triplicate, to facilitate calculation of eGFR using the Schwartz Bedside Formula.
 - f. Day -1 body weight will be used for calculation of the ALN-GO1 or placebo (study drug) dose to be administered during the dosing period.
 - g. Vital signs (blood pressure, pulse rate, body temperature, and respiration rate) will be measured in the supine position after the patient has rested comfortably for 10 minutes. On Day 1 only, vital signs will be measured within 2 hours predose; and 30 (±5 minutes) and 4 hours (±15 minutes) postdose.
 - h. All 12-lead ECGs are triplicate, using centralized equipment. ECGs will be measured approximately 5 minutes apart. Recordings will be obtained after the patient has rested comfortably in the supine position for approximately 10 minutes. Patients should remain supine between ECGs. On dosing days, ECGs will be measured within 2 hours predose; and at 1 hour (±20 minutes), 2 hours (±20 minutes), and 4 hours (±20 minutes) postdose. On all other days, ECGs should be collected at approximately the same time of day corresponding to the predose collection (±1 hour).
 - i. Echo will be performed during the first visit of the Safety and PD Follow-up Period (Day 197) and approximately every 168 days corresponding with visits to the clinical study center for the duration of the study.
 - j. Pregnancy tests will be performed for women of childbearing potential only. A serum pregnancy test will be performed at Screening or after the onset of menarche if the patient was not of childbearing potential at screening, and urine pregnancy tests will be performed thereafter per the Schedule of Assessments and any time pregnancy is suspected. The results of the pregnancy test must be known before study drug administration. FSH will be measured at Screening only to confirm post-menopausal status.

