 - k. Biochemistry, hematology, coagulation, LFTs, and urinalysis parameters are described in Section 7.5.6. Clinical laboratory tests will be analyzed by a central laboratory. Within 4 days prior to dosing, LFT measurements will be analyzed by a local laboratory and confirmed by a central laboratory. Local clinical laboratory results for LFT measurements must be available and reviewed by the Investigator before study drug administration.
 - l. During Screening and throughout the Dosing Period, abnormal results for troponin I tests should be repeated. During the Dosing Period only, local clinical laboratory results must be drawn within 4 days prior to dosing and available and reviewed by the Investigator before study drug administration. Troponin I levels will be measured on the first day of the Safety and PD Follow-up Period (Day 197), and thereafter, approximately every 168 days for the duration of the study. Troponin I results from Day -1, Day 85, Day 113, Day 197, and for the remainder of the study will be analyzed by a central laboratory. Central laboratory results are not required before study drug administration.
 - m. Drugs of abuse are described in Section 7.5.6.3. Screening for drugs of abuse will be performed for patients who are above the age of legal consent.
 - n. Randomization occurs between Day -1 and Day 1.
 - o. Study drug will be administered via SC injection as described in Section 6.2.2.

-
- p. Blood and urine samples for PK analysis will be collected at the time points listed in [Table 12](#).
 - q. On Day 1, the blood sample for PD analysis must be collected within 2 hours predose. The remaining PD samples should be collected at approximately the same time of day corresponding to the predose collection (± 1 hour), as applicable.
 - r. During the screening period, 24-hour urine collections will be completed at 2 separate time points. The first screening 24-hour (± 30 minutes) urine collection will be used to assess eligibility. The second screening 18-24-hour urine collection will only be initiated after eligibility is confirmed.
 - s. Single, 18-24-hour urine sample collections will be performed. The 24-hour urine collection starting on Day -1 must conclude on Day 1 before administration of the first dose of study drug. The 24-hour urine collection should be completed within 4 days prior to the study visit for Day 29, Day 57, Day 85, Day 113, Day 141, and Day 169, and the Q28D Safety and PD Follow-up visits.

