7.2.1 Single-Blind Dosing Period

In Part B, Safety and PD data during the single-blind period will be summarized for the period starting from the first single-blind study drug date/time up to, and including, Study Day 85 for patients randomized to ALN-GO1, or prior to the first dose of ALN-GO1 for patients randomized to placebo. Patients receiving placebo in all regimen and dose cohorts will be pooled together.

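### As most naturally read, SAP 7.4.7 tabulates echocardiogram changes only for the single-blind period, so quarterly, crossover on-drug and expansion-patient echoes are listed but not tabulated

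*SAP*

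**What the plan says.** SAP Section 7.4.7 plans three echo outputs for Part B: summary statistics for baseline ejection fraction, a tabulation of clinically significant change, and a listing of every echo. The tabulation sentence opens "The number of patients with clinically significant changes in systolic function will be tabulated for each on-study assessment" and continues "separately by ascending ALN-GO1 dose level and regimen and placebo for the single-blind dosing period". No other period is named.

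SAP Section 7.2.1 defines that period as running "up to, and including, Study Day 85 for patients randomized to ALN-GO1", "or prior to the first dose of ALN-GO1 for patients randomized to placebo".

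Four other places bear on this:

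- Protocol Section 8.2 commits to combining and summarizing all Part B safety data from the ALN-GO1 dosing period, whatever the treatment sequence. Data from beyond the dosing period may be either summarized or listed.
- Protocol Section 8.2.7 promises echo data in a by-patient listing. SAP Section 7.4 goes further and counts echocardiograms among the safety data to be summarized.
- SAP Section 7.4.6 names five separate Part B periods for ECGs, and Section 7.4.3 sends laboratory data to the Section 7.2 display.
- SAP Section 9 reports no change from the protocol's analysis.

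**The concern.** Safety and tolerability are the primary objective. Echo was added to Part B by Protocol Amendment 3 on the Safety Review Committee's advice, after a trial of another of the sponsor's RNAi products was stopped for a mortality imbalance in which the deaths were primarily cardiac. The echo table is the only planned count of patients whose systolic function changed.

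If that table stops at the end of the single-blind period, it stops before most of the on-drug echoes take place. Its quarterly columns would contain nothing, although the sentence asks for results by regimen. Placebo patients who switch to active drug would contribute only their off-drug echo. A reader of the report would have to assemble the on-drug picture from the listing.

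**Working it through.** No sample-size or power figure is involved. The check maps each scheduled echo to a study day and compares it with the single-blind window.

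**Step 1: echo days.** Protocol Table 2 (monthly) marks screening, Day 85 and Day 169, then about every 168 days. Table 3 (monthly placebo patients after switching) marks Day 85, Day 169 and Day 253. Table 4 (quarterly) has marks at screening, one mid-study column and follow-up from Day 197. The mid-study mark is in column 18. Counting from screening as column 1, column 13 is Day 85 and column 18 is Day 113. The troponin row has its two mid-study marks in columns 13 and 18, and its footnote reads "Troponin I results from Day -1, Day 85, Day 113, Day 197, and for the remainder of the study". The two sources agree, so the quarterly mid-study echo is Day 113 and there is none at Day 85.

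**Step 2: compare with the window.** For patients who switch, day on ALN-GO1 = study day − 85 + 1, taking the first active dose on Day 85.

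| Group | Scheduled post-screening echoes | Inside single-blind period | On drug and inside | Echoes outside, as day on ALN-GO1 |
|---|---|---|---|---|
| Monthly, randomized to ALN-GO1 | Days 85, 169 | 1 | 1 | 169 |
| Monthly, placebo then ALN-GO1 | Days 85 (predose), 169, 253 | 1 | 0 | 169 − 85 + 1 = 85; 253 − 85 + 1 = 169 |
| Quarterly, randomized to ALN-GO1 | Days 113, 197 | 0 | 0 | 113; 197 |
| Quarterly, placebo then ALN-GO1 | Days 113, 197 | 0 | 0 | 113 − 85 + 1 = 29; 197 − 85 + 1 = 113 |
| Expansion (open-label; monthly assumed) | Days 85, 169 | 0 (no such period) | 0 | 85; 169 |

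All quarterly patients receive open-label ALN-GO1 on Day 85, so Day 113 lies after the window in both arms.

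**Step 3: where the missed echoes belong.** SAP Section 7.2.2 sets the ALN-GO1 dosing period at Days 1 to 85 on drug for monthly patients and for quarterly patients who started on placebo, and at Days 1 to 169 for quarterly patients randomized to ALN-GO1. The crossover Day 169 echo, both quarterly Day 113 echoes and the expansion Day 85 echo therefore all fall in the dosing period, which Protocol Section 8.2 says will be summarized. The later echoes (monthly Day 169, crossover Day 253, quarterly Day 197) fall in follow-up periods, where the protocol accepts a listing.

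**Step 4: size.** Neither document fixes the mix of cohorts. As an illustration, take the shells in SAP Section 7.2.3: two monthly and two quarterly cohorts of 4 (3 active, 1 placebo), with 0 or 8 monthly expansion patients, for 16 or 24 patients. Count echoes through the end of postdose follow-up.

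- Inside the window: 6 monthly active + 2 monthly placebo = 8, of which 6 are on drug.
- Outside: 2 crossover + 8 quarterly = 10, or 10 + 8 = 18 with expansion patients. All are on drug.
- Share of all echoes outside: 10/18 = 56%, or 18/26 = 69%.
- Share of on-drug echoes outside: 10/16 = 63%, or 18/24 = 75%.
- Adding one follow-up echo per patient: (10 + 16)/(18 + 16) = 26/34 = 76%, or (18 + 24)/(26 + 24) = 42/50 = 84%.

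**Step 5: a boundary effect.** The monthly Day 85 visit has a window of ±4 days. Read literally, an echo done on Days 86 to 89 in a patient randomized to ALN-GO1 would miss even the single-blind table.

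**The case against.** The strongest reply is that the sentence can be read more broadly. The period phrase could attach to placebo alone, since pooled placebo data exist only in that period. The narrow reading also leaves one scheduled post-baseline visit (monthly Day 85), which sits oddly with a promise to cover each on-study assessment by regimen. SAP Section 7.2.3 says in general terms that Part B by-visit safety summaries follow its shells, which include combined ALN-GO1 columns and run to Day 309. This reading is possible. But Section 7.4.7 neither names the later periods nor cites Section 7.2.3, while the neighbouring ECG and laboratory sections do name or cite theirs. A programmer working from the sentence as written would most likely stop at the single-blind period.

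The second reply is that nothing is lost. Every echo is listed, Protocol Section 8.2.7 promised no more than that, and with at most 24 patients a listing can be read in full. Clinically significant echo changes must also be raised with the Medical Monitor, and adverse events are tabulated through the end of study for everyone who receives ALN-GO1. All of this stands and limits the consequence. It does not reconcile the table with the general commitment in Protocol Section 8.2, and not every echo change need become an adverse event.

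Third, leaving crossover on-drug data out of a single-blind table is correct by definition. That also stands. The issue is that no second table is specified.

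**Conclusion.** The point holds for echo tabulation. As most naturally read, SAP 7.4.7 counts no scheduled post-baseline echo in quarterly cohorts, no on-drug echo in monthly crossover patients and no echo in expansion patients. In the illustrative layout, 63% to 75% of on-drug echoes through postdose follow-up are left out, and every one of those lies in the ALN-GO1 dosing period. This does not fit the sentence's own coverage of each on-study assessment, Protocol Section 8.2, or the ECG handling in SAP 7.4.6.

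A reader might infer that much of the cardiac monitoring goes unsummarized, or that echo results disappear. The documents support neither inference. ECGs are summarized for all Part B periods, troponin I is a laboratory test under the Section 7.2 display, baseline ejection fraction is summarized, and all echoes are listed.

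The zero counts rest on the narrow reading of the period phrase and on the column positions in Table 4, which the troponin footnote corroborates. The percentages depend on the assumed cohort mix. The number of follow-up echoes depends on how many patients move to the extension study. The quarterly Day 113 and crossover Day 169 echoes come before the end of postdose follow-up, so rollover does not remove them.

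**What to change.** In SAP 7.4.7, keep the single-blind comparison with pooled placebo where echoes exist. Add a tabulation of clinically significant change in systolic function for the ALN-GO1 dosing period and for the follow-up periods of Section 7.2.2. Present it by regimen and dose level, combine patients across treatment sequences, and include expansion patients. Two details would make it workable: assign echoes to periods by scheduled visit, so that the ±4-day window does not drop a Day 85 echo, and show the number of patients with an echo at each visit as the denominator. If the broader reading was intended all along, the same sentence makes that explicit.

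The cost is one sentence in the SAP and one extra descriptive table. The data are already collected and listed, and no visit or assessment changes.
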